#### **4.2. Exclusion Criteria**

Subjects presenting with any of the following will not be included in the study:

1. Subject has not successfully completed either Protocol Fx-006 or Fx1A-201.
2. Chronic use of non-protocol approved non-steroidal anti-inflammatory drugs (NSAIDs), defined as greater than 3 to 4 times/month. The following NSAIDs are allowed: acetylsalicylic acid, etodolac, ibuprofen, indomethacin, ketoprofen, nabumetone, naproxen, nimesulide, piroxicam, and sulindac.
3. If female, subject is pregnant or breast feeding.
4. Clinically significant medical condition that, in the opinion of the investigator, would place the subject at an increased risk to participate in the study.
5. An ALT and AST value >3X ULN that in the medical judgment of the investigator is due to reduced liver function or active liver disease.
6. The subject has received a liver or heart transplant at time of enrollment.
7. Sexually active males with partners of childbearing potential not using highly effective contraception or not agreeing to continue highly effective contraception for at least 3 months after last dose of investigational product

#### **4.3. Life Style Guidelines**

##### **4.3.1. Contraception**

Females must be postmenopausal, surgically sterilized or willing to use two acceptable methods of birth control. All female subjects who, in the opinion of the investigator, are biologically capable of having children and are sexually active, must agree to use two effective method of contraception consistently and correctly for the duration of the active treatment period and for 3 months after the last dose of investigational product. The investigator, in consultation with the subject, will select the most appropriate method of

---

contraception for the individual subject (ie.; hormonal contraception, intra-uterine device, diaphragm with spermicide, condom with spermicide; a condom alone is not considered an acceptable method of birth control). The investigator, at each study visit, will confirm and document consistent and correct use. In addition, the investigator will instruct the subject to call immediately if the selected birth control method is discontinued or if pregnancy is known or suspected.

All sexually active male subjects with partners of childbearing potential must agree to use a highly effective method of contraception consistently and correctly for the duration of the active treatment period and for at least 3 months after the last dose of investigational product. The investigator, in consultation with the subject, will select the most appropriate method of contraception for the individual subject. The investigator, at each study visit, will confirm and document consistent and correct use. In addition, the investigator will instruct the subject to call immediately if the selected birth control method is discontinued or if pregnancy is known or suspected.

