### **Inclusion Criteria:**

- Evidence of a personally signed and dated informed consent document indicating that the subject (or a legal representative) has been informed of all pertinent aspects of the study.
- Subject has successfully completed either Protocol Fx-006 or Fx-1A-2011.
- If female, subject is post-menopausal, surgically sterilized, or willing to use an acceptable method of birth control (ie, hormonal contraceptive, intra-uterine device, diaphragm with spermicide, condom with spermicide) throughout the study and for 3 months from the end of the study. (A condom alone is not considered an acceptable method of birth control).

- Male or female subjects with TTR-FAP who have not undergone liver or heart transplantation at time of enrollment and who have successfully completed Protocol Fx-006 or Protocol Fx1A-201.

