Generally, there were no significant toxicities observed in the repeated dose toxicology studies in the rat and dog. Therefore, tafamidis was considered to be well tolerated in the rat at dose levels up to 30 mg/kg/day for 26 weeks, providing an exposure ratio of 45- to 63-fold based on the human AUC at steady state, and in the dog at dose levels up to 45 mg/kg/day for 39 weeks providing an exposure ratio of 29- to 36-fold based on the human AUC at steady state. Additionally, there was no evidence for an increased risk of neoplasia at exposures at least 31-fold the human AUC nor was there evidence of any tafamidis-related genotoxicity. With the exception of the reproductive developmental toxicity findings, tafamidis has an excellent nonclinical safety profile.

Refer to the tafamidis Investigator Brochure for further details.

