## 6.2. Study Period

### 6.2.1. Months 3, 9, 15, 21, 27, 33, 39, 45, 51, 57, 63, 69, 75, 81, 87, 93, 99, 105, 111, 117

Subjects will be contacted by telephone, contact is to be made  $\pm$  1 week of scheduled time:

- Assessment of ambulatory status (mPND);
- Ask subjects non-leading questions such as “How do you feel?” and document adverse events;
- Record concomitant medications;
- Ask about possibility of pregnancy;
- Mail 3 month supplies of investigational product following telephone contact;
- These telephone visits can be conducted in person at the clinic at the discretion of the sites.

---

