#### **6.2.2. Months 6, 18, 30, 42, 54, 66, 78, 90, 102, 114**

Subjects will return to the clinic for the following assessments. Visits are to occur  $\pm$  2 weeks of the scheduled time:

- Collect blood/urine samples for laboratory assessments (section [7.3](#));
- Urine pregnancy test (for women of childbearing potential);
- Assessment of ambulatory status (mPND);
- Ask subjects non-leading questions such as “How do you feel?” and record adverse events;
- Record concomitant medications;
- Determine drug compliance and accountability;
- Dispense 3 month supply of investigational product.

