## 7.2. Pregnancy

The end of study visit urine pregnancy test from Protocols Fx-006 and Fx1A-201 will be used as Day 0 (Baseline) for Protocol Fx1A-303/B3461023. If the pregnancy test is positive, the subject will be disallowed. Female subjects of child-bearing potential will be re-tested for pregnancy at every 6-month visit to the clinical unit and will be asked via telephone contact of possible pregnancy at 3-month intervals between clinic visits. A positive pregnancy test will lead to immediate discontinuation of investigational product and from the study. Subjects will also be instructed to notify the site should they become pregnant. In the event of a pregnancy, all investigational product must be discontinued immediately.

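### The inclusion criterion asks women for one contraceptive method while Section 4.3.1 asks for two, and the 3-month period afterwards starts from different dates

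*Protocol*

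**What the plan says.** The female criterion appears in the Protocol Summary (Inclusion Criteria) and again in Section 4.1. A woman who is not past menopause or surgically sterilized must be "willing to use an acceptable method of birth control". Four options are listed: hormonal contraception, an intra-uterine device, a diaphragm with spermicide, or a condom with spermicide. A condom alone does not count. The duty lasts through the study and for 3 months from its end.

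Section 4.3.1 lists the same four options and the same exclusion of a condom alone, but opens with "Females must be postmenopausal, surgically sterilized or willing to use two acceptable methods of birth control". Its second sentence says that women who, in the investigator's opinion, "are biologically capable of having children and are sexually active, must agree to use two effective method of contraception consistently and correctly". Here the duty covers active treatment and the 3 months after the last dose. The section then turns to checking: "The investigator, at each study visit, will confirm and document consistent and correct use".

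All of this is operative text of Protocol Amendment 2. The summary of changes records that Section 4.3.1 was added for clarity. It does not say which number was intended.

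**The concern.** Sites review and document eligibility against Section 4.1, where one method is enough. Section 4.3.1 then binds the same woman to two. A site following 4.1 as written can enroll a woman who does not meet 4.3.1 from her first dose. The check at each study visit also has no agreed standard: one site could record compliance where another records a deviation.

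The rule protects against a risk that the sponsor itself singles out. Section 1.2.3 concludes: "With the exception of the reproductive developmental toxicity findings, tafamidis has an excellent nonclinical safety profile". The same section reports developmental toxicity in rats and rabbits and advises women to avoid pregnancy on treatment. Treatment may last up to 10 years. Pregnancy tests and telephone questions find a pregnancy after exposure has begun; contraception is the preventive step, so its minimum should be stated without ambiguity.

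**Working it through.** The plan gives no figure to reproduce, so the check is a side-by-side reading.

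| Place in Protocol | Methods | Who | Period after treatment |
|---|---|---|---|
| Summary, Inclusion Criteria | one | females not past menopause or sterilized | 3 months from end of study |
| Section 4.1 | one | same | 3 months from end of study |
| Section 4.3.1, first sentence | two | same | not stated |
| Section 4.3.1, second sentence | two | able to have children and sexually active | 3 months from last dose |

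**Number of methods.** Take a sexually active woman able to have children and apply each text:

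- Intra-uterine device only: meets 4.1, does not meet 4.3.1.
- Intra-uterine device plus condom with spermicide: meets both.
- Condom alone: meets neither.

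Only the first case separates the texts. Any woman who meets 4.3.1 also meets 4.1, but not the reverse. The number two is not a single slip, because 4.3.1 states it twice. Later sentences of 4.3.1 do return to the singular when they describe choosing a method and reporting that it has been stopped, so the section leaves some doubt about intent.

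**Period after treatment.** The two end dates differ by the gap between a woman's last dose and her end of study. For most women the end-of-study visit comes when treatment stops, so the gap should be small. Section 6.3 gives the exception. A liver-transplant recipient stops the product but stays in the study with annual visits, so one such visit alone can put about a year between the two dates, and several visits would put years between them.

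The last dose is the date tied to exposure. Section 1.2.4 gives an average half-life of 59 hours. Taking 3 months as 90 days, 90 × 24 = 2,160 hours, and 2,160 / 59 = 36.6 half-lives. On that average, counting from the last dose covers elimination.

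**Comparison with the male rule.** Section 4.2, item 7, and the male paragraph of 4.3.1 agree: both require highly effective contraception for at least 3 months after the last dose. Only the female rule is out of step.

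**Effect on the analyses.** SAP Section 5.4 keeps subjects with protocol deviations in both the ITT and safety summaries. Protocol Section 9.9 only lists pregnancy test results. No planned analysis uses the number of contraceptive methods.

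**The case against.** The strongest reply is that the two texts do different jobs. Section 4.1 screens willingness at entry and 4.3.1 governs conduct. Nothing in 4.1 says that one method is enough on treatment, so both apply and the stricter one decides. This stands in part: a reader might infer that the texts cannot both be obeyed, and that is wrong, because two methods satisfy both. It does not remove the mismatch, because a woman willing to use only one listed method still passes entry.

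A second reply concerns timing. The original protocol dates from June 2009 and Section 4.3.1 arrived in June 2012, so many women may already have been enrolled and the entry criterion may be largely spent. That is plausible, but the documents give no enrollment dates. If it is true, telling sites what applies to enrolled women matters more than rewording the entry criterion.

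A third reply is that other safeguards remain. Pregnancy is an exclusion. The telephone contacts carry the instruction "Ask about possibility of pregnancy". Urine tests are done at Day 0, at the 6-month visits and at the end of study. And "A positive pregnancy test will lead to immediate discontinuation of investigational product and from the study". This stands, and it is why the point is minor.

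A reader might also infer that one listed method is inadequate, or that women have been harmed. The documents show neither. Nor do they support a separate conflict over sexual activity: the second sentence of 4.3.1 reads naturally as qualifying the first, and a woman who is not sexually active can still be willing to use contraception.

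**Conclusion.** The inconsistency is real and minor. The entry criterion sets a minimum of one method and Section 4.3.1 sets two, from the same list, with no text to reconcile them. The female period after treatment is also counted from two different dates. This rests on the wording alone and needs no assumption about how sites behave.

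The number of women affected cannot be determined. Enrollment of 110 is a ceiling, and the documents give neither the number of women able to have children nor the methods they use. Any head-count would rest on an invented share.

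No harm is demonstrated, and no endpoint, analysis or conclusion is affected. What remains is a cheap correction to a subject-protection rule for a drug with known developmental toxicity in animals.

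**What to change.** State one number of methods in the Protocol Summary, Section 4.1 and Section 4.3.1. The default should be two, so that eligibility matches the stricter rule. That choice is made for caution and is not evidence of what the sponsor meant. If one method was intended, correct both sentences of 4.3.1 instead. If two is kept, put the later singular wording of 4.3.1 into the plural.

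Count the female 3 months from the last dose in all three places, as for males. Send sites a note so that women already enrolled are covered.

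Do not narrow the inclusion criterion to sexually active women. Fixing the number does not require it, and it would loosen an existing safeguard.

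The cost is a clarifying amendment and the site note. Some women using a single method would have to add a second. Counting from the last dose would also shorten the written duty for a woman who stays in the study off drug, for example after a liver transplant. No analysis changes.

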## **5. STUDY TREATMENTS**

### **5.1. Allocation to Treatment**

This is an open-label, single-treatment study. All enrolled subjects will be assigned to receive a single oral daily dose of 20 mg Tafamidis.

### **5.2. Drug Supplies**

#### **5.2.1. Formulation and Packaging**

Tafamidis meglumine (tafamidis), d-glucitol, 1-deoxy-1-(methylamino)-, 2-(3,5-dichlorophenyl)-6-benzoxazolecarboxylate (1:1), is the salt form of 2-(3,5-dichloro-phenyl)-benzoxazole-6-carboxylic acid, or tafamidis (Fx-1006), the free acid. The only active ingredient in tafamidis meglumine is tafamidis.

The tafamidis meglumine drug product will be supplied by the Sponsor as opaque 12 oblong soft gelatin capsules filled with a suspension containing 20 mg of tafamidis meglumine.

Investigational product will be supplied in 10-count child resistant blisterpacks. Investigational product labels will contain the appropriate country-specific information in accordance with relevant regulatory requirements.

#### **5.2.2. Preparation and Dispensing**

Investigational product will be dispensed to subjects according to the following schedule:

- On Day 0 (Baseline), an initial 3-month supply of investigational product will be dispensed to subjects at the clinical unit. Subjects will take their first dose of investigational product at home beginning on Day 1 (ie, first dose).

---

- At 3-month intervals between clinic visits, 3-month supplies of investigational product will be mailed from the clinical site directly to subjects at home.
- Every 6 months, subjects will return to the clinical unit and will be instructed to bring all investigational product and packaging with them to determine investigational product compliance and accountability. At these clinic visits, 3-month supplies of investigational product will be dispensed directly to subjects for self-administration at home.

### **5.2.3. Administration**

All enrolled subjects will self-administer a once-daily oral dose of 20 mg tafamidis at home as instructed by the clinical staff. All investigational product is to be taken by mouth, with water. Subjects will be instructed to take investigational product at the same time each day throughout the treatment period.

Medication errors may result, in this study, from the administration or consumption of the drug by the subject at the wrong time, or at the wrong dose strength. Such medication errors occurring to a study participant are to be captured on the adverse event (AE) page of the CRFs and on the SAE form when appropriate. In the event of medication dosing error, the sponsor should be notified immediately.

Medication errors are reportable irrespective of the presence of an associated AE/SAE, including:

- Medication errors involving subject exposure to the product.
- Potential medication errors or uses outside of what is foreseen in the protocol that do or do not involve the participating subject.

Whether or not the medication error is accompanied by an AE, as determined by the investigator, the medication error and, if applicable, any associated adverse event(s) is captured on an adverse event (AE) CRF page (refer to **ADVERSE EVENT REPORTING** section for further details).

### **5.2.4. Compliance**

All investigational product will be self-administered by subjects at home. Subjects should be instructed to bring all investigational product and packaging to each follow-up visit to the clinical unit every six months. Compliance to investigational product will be determined through capsule counting procedures at subject visits to clinic. Compliance will be monitored and recorded in each subject's case report form (CRF). Additionally, investigational product accountability audits will be performed by the study monitor during routine monitoring visits.

---

### **5.3. Drug Storage and Drug Accountability**

All investigational product (tafamidis) should be stored at controlled room temperature 15-25°C (59-77°F). Investigational product should be stored in its original package and should be protected from light.

Storage conditions stated in the SRSD (Investigator Brochure (IB),) may be superseded by the label storage.

Temperature of storage conditions should be monitored using validated devices that record maximum and minimum temperatures, are regularly calibrated, and data are regularly recorded. Should the product experience temperature excursion, relative to label instruction, during storage, then the impact to product quality and use should be addressed with relevant subject matter experts and documented accordingly.

Occasional short-term excursions from the intended storage conditions may occur. If the duration is short and the deviation in temperature is small, an investigation into the quality of the product is generally not required.

Subjects should be reminded of the storage conditions when drug is dispensed.

### **5.4. Concomitant Medication(s)**

#### **5.4.1. Allowed Medications**

On Day 0, in conjunction with the review of their medical history, all subjects will be asked what medications they are taking. Thereafter, subjects will be asked what medications they have been taking at 3-month intervals (ie, during clinic visits every 6 months and via telephone contact at 3-month intervals between clinic visits). All concomitant medications will be recorded on the CRF.

#### **5.4.2. Medication Restrictions**

The following medications and substances are prohibited during the study, as specified below:

- Chronic use of non-protocol approved non-steroidal anti-inflammatory drugs (NSAIDs), defined as greater than 3-4 times/month. The following NSAIDs are allowed: acetylsalicylic acid, etodolac, ibuprofen, indomethacin, ketoprofen, nabumetone, naproxen, nimesulide, piroxicam, and sulindac.

Of note, in the presence of tafamidis, the plasma protein binding of prednisone was decreased by approximately 10%. As prednisone is rapidly metabolized to the active metabolite, prednisolone, the clinical relevance of these findings are unknown.

---

## 6. STUDY PROCEDURES

Every effort should be made to ensure that scheduled visits are made and protocol required tests and procedures are completed as described. From time to time there may be circumstances, outside of the control of the investigator, which may not make a clinic visit possible. In these cases, and with prior discussion and approval from the sponsor, alternative options may be considered. Approved alternative study visit options will not be considered protocol deviations.

Study procedures are outlined in the [Schedule of Activities](#).

### 6.1. Screening/Baseline Assessment

The end of study physical examination (including weight) and vital sign assessments from Protocols Fx-006 and Fx1A-201 will serve as Day 0 (Baseline) for Protocol Fx1A-303/B3461023 if these examinations were performed within 30 days of Day 0. If more than 30 days has passed between the final study visit of Protocols Fx-006 or Fx1A-201 and Day 0 (Baseline) for Protocol Fx1A-303/B3461023, all Day 0 study procedures will be performed (ie, no data from the final study visits from the previous studies will be utilized). For subjects who successfully completed Protocol Fx1A-201, the NIS, Norfolk QOL-DN, and Karnofsky scores from the end of study visit of Protocol Fx1A-201 will serve as Day 0 (Baseline) assessments for Protocol Fx1A-303/B3461023 if these procedures were performed within 30 days of Day 0. For subjects who successfully completed Protocol Fx-006, the Norfolk QOL-DN from the end of study visit from Protocol Fx-006 will serve as Day 0 (Baseline) if it was performed within 30 days of Day 0. In addition, the cranial nerve and upper limb components of the NIS will be performed on Day 0 and combined with the NIS-LL data from the end of study visit from Protocol Fx-006 and the Karnofsky Performance Scale Index will be assessed on Day 0 of Protocol Fx1A-303/B3461023.

Subjects will be required to sign an informed consent form before beginning participation in Protocol Fx1A-303/B3461023. The following procedures will be performed on Day 0:

- All inclusion and exclusion criteria will be reviewed to ensure eligibility for participation in this study;
- Demographics (date of birth, age, gender, and race) for all subjects will be collected;
- A complete medical history will be obtained;
- Urine test for pregnancy (women of child bearing potential only);
- Complete physical exam including weight and vital signs (if not conducted within 30 days of Day 0);
- NIS;

---

- For subjects who completed Fx1A-201, only if not performed within 30 days of Day 0;
- For subjects who completed Fx-006, the cranial nerve and upper limb components will be performed on Day 0 and combined with the NIS-LL from end of study visit from Fx-006, if performed within 30 days of Day 0. Otherwise all three components of NIS will be performed on Day 0.
- Norfolk QOL-DN, only if not performed within 30 days of Day 0.
- Karnofsky Performance Scale Index.
- For subjects completing Fx1A-201, only if not performed within 30 days of Day 0.
- Adverse events;
- Concomitant medications;
- Dispense 3 month supply of investigational product with instructions that subject is to administer the first dose at home on the following day as instructed (Section 5.2.3).

